13.1.4 Safety Analysis

Safety will be assessed by summarizing the incidence of AEs, clinical laboratory values, gastrin levels, ECG, and vital signs.

Summary of AEs, ECG results, clinical laboratory values, gastrin levels, and vital signs will be provided separately for the Healing Period and for the Maintenance Period. For the Healing Period, baseline values will be the last available assessment before the first dose of study drug. The baseline values for the Maintenance Period will be the assessment performed at the Week 8 visit of the Healing Period.

All AEs will be coded using MedDRA. Treatment-emergent adverse events (TEAE) will be summarized using preferred term and primary system organ class overall, by severity, and by relationship to study drug for each treatment group. Separate summaries will also be generated for treatment-related adverse events (TRAEs) overall and by severity. AEs that were reported more than once by a subject during the same period will be counted only once for that subject and period at the maximum severity.

Other safety assessments (ECG results, clinical laboratory values, gastrin levels, and vital signs) will be summarized by double-blind treatment group at all visits assessed using descriptive statistics. Values outside the reference ranges and markedly abnormal laboratory values will be flagged and tabulated.

13.2 Determination of Sample Size

A total of 450 subjects with EE documented during Screening are planned to be enrolled into this study. Approximately 300 subjects are expected to enter the Maintenance treatment period.

Assuming a 10% dropout rate during the Healing Period and an 85% healing rate at Week 8 for both lansoprazole and dexlansoprazole, 225 subjects per arm will provide at least 80% power at the 1-sided 0.025 level of significance to meet the noninferiority criteria between lansoprazole and

dexlansoprazole. Noninferiority to lansoprazole will be declared if the lower bound of the confidence interval for the difference in healing rates is greater than -10%.

The fixed noninferiority margin of -10% is based on a double-blind, parallel-group, comparative study that evaluated EE healing rates after an 8-week treatment period with lansoprazole 30 mg QD or placebo. In this study, the difference in response rate between the lansoprazole 30 mg dose group and the placebo group was 40.4%; the lower limit of the 2-sided 95% confidence interval was 25.9%. Hence, even with a conservative assumption of this lower bound as the treatment effect of lansoprazole 30 mg, a -10% noninferiority margin would assure that dexlansoprazole 30 mg retains more than 60% of the treatment effect of lansoprazole 30 mg [22].

Assuming a 33% dropout rate during the Maintenance Period and that maintenance rates are 14% and 66% for placebo and dexlansoprazole 30 mg, respectively, 150 subjects per arm will have at least 99% power at the 2-sided 0.05 level of significance to detect a difference between the treatment groups.

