At the Week 8 Visit, all subjects will undergo a physical examination including vital signs, laboratory evaluations, fasting serum gastrin, serum and urine pregnancy test (all women of childbearing potential), ECG and an endoscopy. In addition, study drug will be collected, a review of concomitant medication use will be performed, and an assessment of AEs will be conducted. If the subject's EE has healed completely as determined by endoscopy, the subject will have completed the Healing Period of the study, and will continue in the Maintenance Period. If the subject's EE has not completely healed after 8 weeks of treatment, all Final Visit procedures will be performed and the subject will not be eligible to continue into the Maintenance Period.

For subjects who prematurely discontinue during the Healing Period, efforts should be made to perform all procedures scheduled for the Week 8 / Early Termination Visit no later than 5 days after the last dose of study drug.

At the start of the 6-Month Maintenance Period, subjects with healed EE will be randomized in a 1:1 ratio to one of the following 2 groups; the randomization will be stratified by baseline endoscopic findings (grades A/B or C/D).

- Group I: dexlansoprazole capsules (30 mg QD)
- Group II: placebo (QD)

During the 6-month Maintenance Period, study drug will be self-administered orally, QD in the morning before breakfast. Subjects will continue to document the presence and maximum severity of daytime and nighttime heartburn symptoms using a diary. Subjects will also record the use of rescue medication. Subject visits will be conducted at Months 1, 3 and 6, of the Maintenance Period to collect and/or dispense study drug, assess GERD symptoms, review concomitant medication use, and assess AEs. Endoscopies will be performed at Months 1 and 6/Final Visit to evaluate maintenance of healed EE. Subjects with endoscopic evidence of relapsed EE will be discontinued from the study.

At the Month 1 Visit, the subject will undergo a physical examination including vital signs, laboratory evaluations, endoscopy, and urine pregnancy test (all women of childbearing potential).

[figure not shown]

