13.1.1 Analysis Sets

The full analysis set (FAS) will be defined separately for the Healing and Maintenance Periods. The full analysis set for the Healing Period (FAS – H) will include all randomized subjects who have documented EE at screening and receive at least 1 dose of study drug during the first 8 weeks of treatment. The full analysis set for the Maintenance Period (FAS – M) will include all subjects with healed EE by week 8 who are randomized and receive at least 1 dose of study drug during 6 months of maintenance treatment.

The safety analysis set will be defined separately for the healing period and for the Maintenance Period. The safety analysis set for the Healing Period (Safety Set – H) will include all subjects who receive at least 1 dose of study drug during Healing Period. The safety analysis set for the Maintenance Period (Safety Set – M) will include all subjects with healed EE by Week 8 who are randomized and receive at least 1 dose of study drug during 6 months of maintenance treatment.

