13.1.3 Efficacy Analysis

The primary efficacy variable will be the percentage of subjects who have complete healing of EE over 8 weeks as assessed by endoscopy. The treatment difference of healing rate between dexlansoprazole and lansoprazole will be calculated and the lower bound of 95% confidence interval will be compared with -10%. Noninferiority to lansoprazole will be declared if the lower bound is greater than -10%. Subjects who do not have endoscopically documented healing and who prematurely discontinue will be considered as not healed.

The secondary efficacy variable will be the percentage of subjects who maintained complete healing of EE over 6 months as assessed by endoscopy. A comparison between dexlansoprazole capsules and placebo will be made using Cochran-Mantel-Haenszel (CMH) test using

stratification factor of baseline grade. Subjects who do not have endoscopically documented maintenance of healing and who prematurely discontinue will be considered to have relapsed.

An additional efficacy variable will be the severity of GERD symptoms at Weeks 4 and 8 as assessed by the investigator during the Healing Period. The severity of GERD will be compared between dexlansoprazole and lansoprazole capsules using a CMH test for ordered responses with baseline severity as the stratum. The number of subjects at each severity level for each GERD symptom at Months 1, 3, 6 will be also summarized by treatment group and baseline severity. At each visit, the severity will be compared between treatment groups using a CMH test for ordered responses (row mean score statistic with table scores of 0, 1, 2, 3, and 4) with baseline severity as the strata.

The percentage of days with neither daytime nor nighttime heartburn and the percentage of days without rescue medication use over the 8 weeks of the Healing Period and over the 6 months of the Maintenance Period as assessed by the daily diary will be summarized by treatment groups. Comparisons between treatment groups will be made using Wilcoxon rank-sum tests.

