7.1.1 Definition of Study Days and Visit Window

Study day will be calculated relative to the date of the first dose of study drug in the study. The study day prior to the first dose of study drug will be calculated as:

$$\text{Date of assessment/event} - \text{date of first dose of study drug.}$$

The study day on or after the first dose of study drug will be calculated as:

$$\text{Date of assessment/event} - \text{date of first dose of study drug} + 1.$$

Baseline is defined as the last non-missing measurement prior to or on Study Day 1 (prior to first dose). The baseline values for the Maintenance Period will be the assessment performed at the Week 8 visit of the Healing Period. The visit windows for each post baseline visit are defined in [Table 7.a](#). If a subject has more than 1 measurement in the same visit window, the measurement closest to the scheduled visit will be used. If 2 measurements in the same window are of equal distance to the scheduled visit, the measurement that occurs after the scheduled visit will be used. If 2 or more measurements occur on the same day, the last value obtained will be used.

Table 7.a Visit Windows for Healing Period

Visit	Scheduled Day	Safety Labs	Serum Gastrin	Vital Signs	ECG	Endoscopy	GERD Symptoms Investigator Assessment
Baseline	Day -1	≤1	≤1	≤1	≤1	≤1	≤1
Week 4	Day 28	2-42	NA	2-42	NA	NA	2-42
Week 8	Day 56	43-70	2-70	43-70	NA	2-70	43-70

Note: Safety labs (including gastrin), vital signs, and ECG data obtained more than 7 days after the last day of study drug and efficacy data obtained more than 7 days after the last day of study drug will not be included in the analyses.

Additionally, for subjects with healed EE by Week 8 who are randomized and receive at least 1 dose of maintenance study drug, the window selection for the Week 8 Visit will include only measurements assessed on or before the date of the first dose of maintenance period study drug; for visits during the Maintenance of Healed EE Period, the window selection will only include measurements assessed after the date of the first dose of maintenance period study drug.

The summary of visits during the maintenance period will be relative to the start of maintenance treatment rather than relative to the start of the study. The table below summarizes the visit windows for each visit during the Maintenance of Healed EE Period.

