7.8 Efficacy Analysis

The efficacy endpoints will be summarized using the FAS-H for the healing period and using the FAS-M for the maintenance period.

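### Does the primary power statement fail because the plan does not say which population the 85% healing rate describes, or how the 10% dropout is used?

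*Protocol*

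**What the plan says.** The sample size section (Protocol 13.2, with the same text in Protocol 2.0 and SAP 6.0) sets out the inputs as "Assuming a 10% dropout rate during the Healing Period and an 85% healing rate at Week 8 for both lansoprazole and dexlansoprazole" and concludes that "225 subjects per arm will provide at least 80% power at the 1-sided 0.025 level of significance". The margin is 10 percentage points.

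The analysis it serves is in Protocol 13.1.3: "The treatment difference of healing rate between dexlansoprazole and lansoprazole will be calculated", and the lower 95% confidence limit is compared with -10%. Dropouts are covered by a rule: "Subjects who do not have endoscopically documented healing and who prematurely discontinue will be considered as not healed". Protocol 13.1.1 defines the analysis population, FAS-H, which "will include all randomized subjects who have documented EE at screening and receive at least 1 dose of study drug" in the healing period. SAP 7.8 confirms it: "The efficacy endpoints will be summarized using the FAS-H for the healing period". Neither document defines a per-protocol or completer set.

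Two provisions decide whether a dropout can still count as healed. Protocol 6.1 says: "For subjects who prematurely discontinue during the Healing Period, efforts should be made to perform all procedures scheduled for the Week 8" or early termination visit within 5 days of the last dose, and those procedures include endoscopy. SAP 7.1.1 accepts a Week 8 endoscopy from Day 2 to Day 70 and adds that "efficacy data obtained more than 7 days after the last day of study drug will not be included in the analyses". An endoscopy within 5 days of the last dose falls inside that 7-day limit.

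**The concern.** When dropouts stay in the denominator and mostly count as failures, dropout lowers the response rate and leaves n alone. The planned 225 per arm, however, looks like a number reached the other way: find n for 85% healing, then divide by 0.9. If that is what was done, and if 85% was meant for subjects who finish eight weeks, the quoted power belongs to an analysis that will not be run. The real FAS-H healing rate would be below 85%, its variance larger, and the power below 80%.

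At stake is the chance of missing noninferiority when the two drugs are truly equal. The plan implies 20% or less. On the completer reading it would be about 22% if half of the dropouts have documented healing, and about 29% if none do.

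**Working it through.** **Inputs.** Margin 0.10, one-sided alpha 0.025 (z = 1.96), 225 per arm, 85% healing in both arms, 10% dropout: all from Protocol 13.2. The share f of dropouts with documented healing is not in the documents, so it is varied. The confidence interval method is not named; the main figures use the unpooled normal approximation:

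power = Φ(0.10 / √(2p(1−p)/n) − 1.96)

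**1. Reproducing the plan's figure.** At p = 0.85, 80% power needs n = (1.96 + 0.8416)² × 2 × 0.85 × 0.15 / 0.10² = 200.1, so 201 per arm. Then 201/0.9 = 223.3, so 224, against 225 planned. With 202 per arm left after 10% loss, SE = √(0.255/202) = 0.03553 and power = Φ(2.8145 − 1.96) = 80.4%. The statement reproduces. This is not the only route to it: a continuity-corrected calculation with all 225 gives 81.0%, and there the 10% plays no part. How the sponsor got to 225 is therefore an inference.

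**2. 85% as the FAS-H rate.** SE = √(0.255/225) = 0.03367; power = Φ(2.9704 − 1.96) = 84.4%. The chance of missing noninferiority with equal drugs is about 16%.

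**3. 85% as a completer rate.** The FAS-H rate becomes p = 0.9 × 0.85 + 0.1 × f = 0.765 + 0.1f, with n = 225:

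| Dropouts with documented healing (f) | FAS-H rate | Power |
|---|---|---|
| 0% | 76.5% | 70.6% |
| 25% | 79.0% | 74.0% |
| 50% | 81.5% | 78.0% |
| 75% | 84.0% | 82.5% |
| 85% | 85.0% | 84.4% |

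Power is 80% at p = 0.8266, so f = (0.8266 − 0.765)/0.1 = 62%.

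**4. Sensitivity to method, n = 225.**

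| Method | p = 0.85 | p = 0.815 | p = 0.765 |
|---|---|---|---|
| Unpooled normal | 84.4% | 78.0% | 70.6% |
| Exact enumeration, Wald limit | 84.4% | 78.3% | 70.8% |
| Farrington-Manning | 83.2% | 77.3% | 70.4% |
| Continuity-corrected | 81.0% | 74.2% | 66.7% |

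With all of FAS-H kept and 85% as its rate, every method gives at least 81%. With 202 per arm the result sits on the boundary: 80.4% unpooled, 80.6% exact Wald, 79.0% Farrington-Manning, 76.3% continuity-corrected.

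**5. Which reading the text supports.** Protocol 13.1.3 compares healing rates with undocumented discontinuers counted as not healed. Protocol 13.2 uses the same term for its 85% and for the difference tested against the margin. Nowhere is 85% called a completer rate, and there is no completer population for it to describe. The FAS-H reading is the natural one.

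**The case for a change.** The strongest case for a change is that the two readings fall on opposite sides of the stated 80%, for the trial's only primary endpoint, and that one clause would settle the matter. The near match of 201/0.9 to 225 suggests that dropouts were taken out of n, although FAS-H retains them. Early-termination endoscopy is only to be attempted, so a high share of documented healing among dropouts cannot be taken for granted. A different choice of confidence interval does not lift the completer figures for f of 50% or less above 80%.

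The ambiguity is real, and the figures are right. But dividing by 0.9 does not show that 85% was a completer rate. Applied to a FAS-H rate it is simply an allowance on the safe side, and FAS-H can lose a few randomized subjects who never take a dose. The completer shortfall also depends on holding f below about 62%. No passage supports a ceiling of 50% or any other figure, and the plan's provisions for early endoscopy let documented healing count. The most that can be said is that power might be below 80% under assumptions that the plan does not state.

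A side question is why only about 300 subjects are expected in the Maintenance Period when the assumptions give 450 × 0.9 × 0.85 = 344 healed completers. More entrants would only raise a power already put at 99% or more, so nothing turns on it.

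**Conclusion.** The concern does not call for a change. The claim of at least 80% power is not an arithmetic error. It reproduces at 80.4% with dropouts removed, and it is 84.4% for the planned FAS-H analysis when 85% is read as Protocol 13.1.3 uses the term. It fails only if 85% is a completer rate and fewer than about 62% of dropouts have documented healing; the extreme case, with none, gives 70.6%.

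These figures assume equal true healing rates, equal dropout and equal documented healing in both arms, and that all 225 per arm are dosed and have documented EE. Naming the population would make the sentence clearer, but it is missing detail that a reader can fill from the efficacy section. Neither reading alters the number randomized, the margin, the analysis set, type I error or the rule for declaring noninferiority. Once the data are in, the confidence interval shows the precision achieved, whatever rate was assumed in planning.

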14.0 QUALITY CONTROL AND QUALITY ASSURANCE

14.1 Study-Site Monitoring Visits

Monitoring visits to the study site will be made periodically during the study to ensure that all aspects of the protocol are followed. Source documents will be reviewed for verification of data recorded on the eCRFs. Source documents are defined as original documents, data, and records. The investigator and institution guarantee access to source documents by the sponsor or its designee (CRO) and by the IRB or IEC.

All aspects of the study and its documentation will be subject to review by the sponsor or designee (as long as blinding is not jeopardized), including but not limited to the Investigator's Binder, study medication, subject medical records, informed consent documentation, documentation of subject authorization to use personal health information (if separate from the informed consent forms), and review of eCRFs and associated source documents. It is important that the investigator and other study personnel are available during the monitoring visits and that sufficient time is devoted to the process.

14.2 Protocol Deviations

The investigator should not deviate from the protocol, except where necessary to eliminate an immediate hazard to study subjects. Should other unexpected circumstances arise that will require deviation from protocol-specified procedures, the investigator should consult with the medical monitor (and IRB or IEC, as required) to determine the appropriate course of action. There will be no exemptions (a prospective approved deviation) from the inclusion or exclusion criteria.

The site should document all protocol deviations in the subject's source documents. In the event of a significant deviation, the site should notify the sponsor or its designee (and IRB or EC, as required). Significant deviations include, but are not limited to, those that involve fraud or misconduct, increase the health risk to the subject, or confound interpretation of primary study assessment. The Significant Protocol Deviation eCRF is to be completed for deviations that are identified as significant by the sponsor.

14.3 Quality Assurance Audits and Regulatory Agency Inspections

The study site also may be subject to quality assurance audits by the sponsor or designees. In this circumstance, the sponsor-designated auditor will contact the site in advance to arrange an auditing visit. The auditor may ask to visit the facilities where laboratory samples are collected, where the medication is stored and prepared, and any other facility used during the study. In addition, there is the possibility that this study may be inspected by regulatory agencies, including those of foreign governments (eg, the Food and Drug Administration [FDA], the United Kingdom Medicines and Healthcare products Regulatory Agency [MHRA], the Pharmaceuticals and Medical Devices Agency of Japan [PMDA]). If the study site is contacted for an inspection by a regulatory body, the sponsor should be notified immediately. The investigator and institution guarantee access for quality assurance auditors to all study documents as described in Section 14.1.

15.0 ETHICAL ASPECTS OF THE STUDY

This study will be conducted with the highest respect for the individual participants (ie, subjects) according to the protocol, the ethical principles that have their origin in the Declaration of Helsinki, and the ICH Harmonised Tripartite Guideline for GCP. Each investigator will conduct the study according to applicable local or regional regulatory requirements and align his or her conduct in accordance with the “Responsibilities of the Investigator” that are listed in [Appendix B](#). The principles of Helsinki are addressed through the protocol and through appendices containing requirements for informed consent and investigator responsibilities.

15.1 IRB and/or IEC Approval

IRBs and IECs must be constituted according to the applicable state and federal/local requirements of each participating region. The sponsor or designee will require documentation noting all names and titles of members who make up the respective IRB or IEC. If any member of the IRB or IEC has direct participation in this study, written notification regarding his or her abstinence from voting must also be obtained. Those US sites unwilling to provide names and titles of all members due to privacy and conflict of interest concerns should instead provide a Federal Wide Assurance Number or comparable number assigned by the Department of Health and Human Services.

The sponsor or designee will supply relevant documents for submission to the respective IRB or IEC for the protocol’s review and approval. This protocol, the Investigator’s Brochure, a copy of the informed consent form, and, if applicable, subject recruitment materials and/or advertisements and other documents required by all applicable laws and regulations, must be submitted to a central or local IRB or IEC for approval. The IRB’s or IEC’s written approval of the protocol and subject informed consent must be obtained and submitted to the sponsor or designee before commencement of the study (ie, before shipment of the sponsor-supplied drug or study specific screening activity). The IRB or IEC approval must refer to the study by exact protocol title, number, and version date; identify versions of other documents (eg, informed consent form) reviewed; and state the approval date. The sponsor will [ship drug/notify site] once the sponsor has confirmed the adequacy of site regulatory documentation and, when applicable, the sponsor has received permission from competent authority to begin the trial. Until the site receives [drug/notification] no protocol activities, including screening may occur.

Sites must adhere to all requirements stipulated by their respective IRB or IEC. This may include notification to the IRB or IEC regarding protocol amendments, updates to the informed consent form, recruitment materials intended for viewing by subjects, local safety reporting requirements, reports and updates regarding the ongoing review of the study at intervals specified by the respective IRB or IEC, and submission of the investigator’s final status report to IRB or IEC. All IRB and IEC approvals and relevant documentation for these items must be provided to the sponsor or its designee.

Subject incentives should not exert undue influence for participation. Payments to subjects must be approved by the IRB or IEC and sponsor.

